***Measurement of primary endpoint: The individual cognitive domain and global cognitive function score***

All enrolled subjects will undergo assessment of cognitive function at (1) enrollment, (2) 1 year and (3) 2 years.

AF may have a greater impact on non-memory cognitive domains such as executive function, thus predisposing to non-amnesic dementia. Hence we will test individual cognitive domains to increase the sensitivity of the tests.

The following standardized tests will be administered at each visit by a trained neuropsychometrist.

Testing of four major cognitive function domains

1. Executive function - Trail Making Test B and Digit Symbol Substitution Test
2. Language - Boston Naming Test and Category Fluency
3. Memory - Logical Memory-II (delayed recall), Visual Reproduction-II (delayed recall) and Auditory Verbal Learning Test (delayed recall)
4. Visuospatial - Picture Completion and Block Design

Questionnaires to rule out competing diagnoses:

1. The Beck Depression Inventory
2. The Beck Anxiety Inventory

An informant, identified by the subject as someone with whom they have contact at least once every week, will be interviewed in person or by telephone to complete the following:

1. Clinical dementia rating scale (CDR)
2. Functional assessment questionnaire

For patients lost to clinic follow-up, assessment of cognitive state will be performed using the following questionnaires administered over the telephone:

Telephone interview of cognitive status (TICS-M) (administered to subject)

2. Clinical dementia rating scale (administered to informant)
3. Functional assessment questionnaire (administered to informant)

***Adjustment of Neurocognitive function scores using normative data and derivation of 'Global cognitive function score'***

The raw scores on each neuropsychological test will be transformed into age- and education-adjusted scores using Mayo's Older American Normative Studies normative data. The adjusted scores within each of the 4 domains will be added to obtain the domain specific score. Since different numbers of tests are used within each domain (i.e., 2 tests for the executive, language, and visuospatial domains versus 3 tests for memory), the domain scores will also be scaled for the number of tests to allow comparisons

across domains. The global cognitive function score will then be derived using an average of the 4 domain specific scores.

The performance of a person in a particular domain and their global performance will then be measured by comparing the person's score with the score in normal person that has been previously established to derive a 'z-score'. These comparisons rely on extensive previous normative work we have performed in assessing the cognitive abilities of the population from which the sample will be derived. The tests and definitions provided here have been previously described in detail by our group. The tests will parallel those used by the NIH funded Mayo Clinic Study of Aging, a large ongoing community based study of cognitive function in Olmsted County, MN.

The 'z-score' in individual cognitive domains and the global cognitive function score will be plotted at each time point for the two treatment groups to assess temporal changes.

### ***Measurement of secondary endpoint: Mild cognitive impairment or dementia***

The CDR score (range 0–3) will be assessed in addition to the results of the neuropsychological testing. A team of Neurologist and Neuropsychometrist will assign a diagnosis of normal cognition or mild cognitive impairment or dementia to each subject at each time point. This team will be blinded to treatment assignments. Each assessment of an individual patient will be assessed independent of prior assessments. The definitions used are as follows:

#### *Dementia*

Subjects with a CDR 1 will be classified as demented if they meet DSM-V criteria for 'major neurocognitive disorder' as follows:

1. Evidence of significant cognitive decline from a previous level of performance in one or more cognitive domains based on:
  - a. Concern of the individual, a knowledgeable informant, or the clinician that there has been a significant decline in cognitive function; and
  - b. A substantial impairment in cognitive performance, preferably documented by standardized neuropsychological testing.
2. The cognitive deficits interfere with independence in everyday activities.
3. The cognitive deficits do not occur exclusively in the context of delirium and are not better explained by another mental disorder.

For subjects with CDR 0.5, a committee of the examining neuropsychologist and physician will critically examine the available tests to determine whether the DSM-V criteria for dementia or MCI are met.

#### *Mild cognitive impairment*

The criteria for diagnosis of MCI are: cognitive concern expressed by a physician, informant, participant or nurse; cognitive impairment in 1 or more domains; normal functional activities and not demented. Subjects with MCI can have a CDR of 0 or 0.5; however, the final diagnosis of MCI will not be based exclusively on the CDR but rather on all available data. A committee of the examining neuropsychologist and physician will critically examine the available tests to determine whether the criteria for MCI are met.

#### *Normal Cognition*

Subjects judged to have no cognitive impairment based on the criteria above and received a CDR of 0, will be considered as cognitively normal.

### **Brain MRI imaging to assess burden of cerebral infarcts and cerebral microbleeds**

#### **MR Imaging of brain**

Cerebral MRI will be performed *without* gadolinium contrast using a 3 Tesla scanner at enrollment and at 2 years. If a subject is withdrawn or withdraws prior to the completion of follow-up, an attempt to obtain MRI prior to withdrawal will be made. The following imaging sequences will be performed per standard protocols at our institution: (1) sagittal T1-weighted, (2) axial T2-weighted fast spin echo (FSE), (3) axial T2-weighted fluid-attenuated inversion recovery (FLAIR), (4) axial gradient echo (GRE), (5) axial diffusion tensor-tracer imaging (DTI), (7) 3-dimensional magnetization prepared rapid gradient-echo (MPRAGE) sequence and (8) Axial SWAN (T2 Star Weighted Angiography).

The MRI will be read by a board certified Radiologist who is blinded to treatment assignment.

A new cerebral infarct will be defined as an unequivocal focus of hyperintensity to gray matter on DTI images. GRE and MPRAGE sequences will be used to quantitate the cerebral microbleeds. Cerebral volume analysis will be performed for total cerebral and hippocampal volume using standardized software. The number, size and location of new cerebral infarcts (cortical vs. subcortical and specific anatomic location of infarct) and cerebral microbleeds (lobar vs subhemispheric and specific anatomic location of infarct) will be determined and documented in a CRF.

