To assess the development of mild cognitive impairment or dementia	
Clinical dementia rating scale
 
Dementia Subjects with a CDR 1 will be classified as demented if they meet DSM-V criteria for ‘major neurocognitive disorder’ as follows:
 
 
1. Evidence of significant cognitive decline from a previous level of performance in one or more cognitive domains based on:               
 
a. Concern of the individual, a knowledgeable informant, or the clinician that there has been a significant decline in cognitive function; and
 
b. A substantial impairment in cognitive performance, preferably documented by standardized neuropsychological testing.
 
 
 
2. The cognitive deficits interfere with independence in everyday activities.
 
3. The cognitive deficits do not occur exclusively in the context of delirium and are not better explained by another mental disorder.
 
 
For subjects with CDR 0.5, a committee of the examining
	The development of dementia or mild cognitive impairment are important end points with clinical relevance to the patient.

OBJECTIVES	ENDPOINTS	JUSTIFICATION FOR ENDPOINTS
	
neuropsychologist and physician will critically examine the available tests to determine whether the DSM-V criteria for dementia or MCI are met.
 
Mild cognitive impairment                      The criteria for diagnosis of MCI are: cognitive concern expressed by a physician, informant, participant or nurse; cognitive impairment in 1 or more domains; normal functional activities and not demented. Subjects with MCI can have a CDR of 0 or 0.5; however, the final diagnosis of MCI will not be based exclusively on the CDR but rather on all available data. A committee of the examining neuropsychologist and physician will critically examine the available tests to determine whether the criteria for MCI are met.
	
Tertiary end points		
MRI detected new cerebral ischemic lesions and cerebral microbleeds (CMBs)	Brain MRI will be performed at baseline and 2 years to assess the presence of new cerebral ischemic lesions on DTI imaging and new cerebral microbleeds on SWAN sequences.	The presence of cerebral infarcts, even clinically silent ones, have been associated with higher future risk of dementia. Similarly, CMBs are associated with dementia and future risk for intracerebral hemorrhage.

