### Specific objectives

*Primary objective: To assess the decline in cognitive function using standardized neurocognitive assessment in patients with atrial fibrillation over the age of 60 years with CHA2DS2-VASc score  $\geq 2$  treated with Apixaban versus warfarin*

Our hypothesis is that Apixaban is associated with reduction in decline of cognitive function scores when compared to dose adjusted warfarin with goal INR of 2 – 3. We will test this hypothesis by randomizing patients with AF over the age of 60 years and CHA2DS2-VASc score  $\geq 2$  to anticoagulation with Apixaban vs Warfarin. The primary endpoint of this study is the longitudinal change in cognitive function scores over a follow-up of 2 years in individual cognitive domains (executive, language, memory and visuospatial) and global cognitive function. The development of mild cognitive impairment or dementia will also be assessed as a secondary end point. By the end of this study it is our expectation that the risk of cognitive impairment in AF patients taking Apixaban compared to Warfarin will be well defined and such results will provide a novel measure to reduce the burden of cognitive impairment in AF.

**Rationale:** Cognitive function scores are chosen as the primary end point due to their sensitivity to detect changes in cognitive function within a short span of time. While dementia is also an important end point, it is increasingly recognized that milder degrees of cognitive dysfunction are more prevalent and may have an important impact on a person's quality of life and morbidity. Early recognition of cognitive decline can lead to earlier intervention to either treat or prevent progression. Hence the primary end point of decline in cognitive function in one or more domains will be a clinically relevant and a patient centered outcome.

*Secondary objective: To determine the incidence of new cerebral infarct and new cerebral microbleeds using cerebral MRI in AF patients treated with Apixaban vs warfarin.*

The secondary objective is to evaluate the impact of Apixaban on subclinical emboli and CMBs detected by brain MRI compared to Warfarin. Our hypothesis is that Apixaban is associated with fewer new subclinical emboli and CMBs, compared to warfarin. This has important clinical implications as reduction in these has significant potential to reduce the risk of cognitive impairment.

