Participants who change OAC treatment during follow-up will be withdrawn from the study. A CRF will collect details of the reason for discontinuation of study intervention. Endpoints will be assessed at the time of withdrawal from the study including MRI and cognitive function. The MRI of the head and / or cognitive assessment will be performed at the time of withdrawal from the study if it is greater than 6 months since their last assessment of MRI and / or cognitive function. If a patient withdraws within 6 months of the last assessment, repeat testing will not be performed and the last assessment will be used for the analysis. Participants who withdraw from the study will be followed for 30 days after withdrawal for adverse events. A primary intention to treat analysis will be performed at the end of the study. Participants who withdraw or change OAC treatment will be censored at the time of withdrawal.

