## 8 STUDY ASSESSMENTS AND PROCEDURES

### 8.1 EFFICACY ASSESSMENTS

#### **Screening assessment**

Screening for eligible participants will be performed using the Mayo medical records by a study coordinator. Only patients who have previously given consent to the use of their medical records for research purposes will be screened. ECG, Holter, telemetry recordings will be reviewed to confirm the diagnosis of AF. Charts will be reviewed to assess eligibility for the study including past medical history, current medications, laboratory tests and calculation of the CHA2DS2-VaSC score. The creatinine will be checked if a measurement within 3 months of enrollment is not available.

Potential participants will be contacted in person or through a letter or on the phone. Interested persons will be interviewed on the phone to confirm eligibility and will have a blood test for creatinine if needed. Once enrolled, subjects will be randomized to one of the study arms and will start study drug.

Baseline assessment of brain MRI will be performed prior to initiation of study drug. Baseline assessment of cognitive function will be performed prior to or within 1 month of enrollment. Subsequent assessments will be performed at 1 and 2 year follow-up or within a 3 month time frame of this date.

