### 9.4 STATISTICAL ANALYSES

#### 9.4.1 GENERAL APPROACH

Continuous and categorical variables will be summarized as mean (standard deviation, SD) and number (%) respectively. Differences between the two treatment arms at baseline will be examined using t-tests for continuous variables and chi-square tests for categorical variables.

The baseline variables include age, sex, education, cardiovascular risk factors (hypertension, diabetes mellitus, hyperlipidemia), past medical history (including stroke, TIA, heart failure, peripheral arterial disease, MI, coronary artery disease, liver disease, renal disease, malignancy), duration of AF, pattern of AF (paroxysmal, persistent), prior h/o anticoagulation (duration and type of drug used), prior treatment of AF (antiarrhythmic drug, ablation procedure), and current medications. This data will be reviewed and updated at each visit. The INR values during the study will be collected for patients on warfarin and the time in therapeutic range calculated using the Rosendaal method of interpolation.

Longitudinal changes in each cognitive domain (language, attention, memory, visual spatial and global) will be analyzed using multiple adjusted linear mixed effects models comparing Apixaban vs warfarin. These models will be adjusted for baseline variables that differ between the groups. These results will be presented as beta estimates for baseline differences in cognitive function score by treatment status, change with time and the effect of treatment on the change in scores over time.

For the secondary end point of dementia/MCI, the mid-point between the most recent visit with a cognitively normal diagnosis and the first visit with a diagnosis of MCI or dementia will be considered the date of onset. Participants who are lost to follow-up or die during follow-up will be censored at the

date of last follow-up. Cox proportional hazards model will be used to assess the secondary end points of MCI/dementia, cerebral infarction and cerebral microbleeds. Adjustment for baseline factors noted above will be performed in the multivariable model.

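### As written, a new infarct is defined only by DTI brightness on a single follow-up scan at 2 years or exit, so the MRI endpoint would count infarcts from shortly before that scan and not 2-year incidence

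*Combined protocol and SAP*

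**What the plan says.** **Definition.** Section 8.1, MR Imaging of brain: "A new cerebral infarct will be defined as an unequivocal focus of hyperintensity to gray matter on DTI images". The endpoint table in Section 3 agrees: "Brain MRI will be performed at baseline and 2 years to assess the presence of new cerebral ischemic lesions on DTI imaging". Neither place gives another sequence a role in identifying infarcts.

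**Schedule.** MRI is done "using a 3 Tesla scanner at enrollment and at 2 years"; there is no 1-year scan. The visit window, if it applies to MRI, is loose: "Subsequent assessments will be performed at 1 and 2 year follow-up or within a 3 month time frame of this date". For early leavers, Section 7.1 says: "The MRI of the head and / or cognitive assessment will be performed at the time of withdrawal from the study", provided the last one is more than 6 months old. That scan takes the place of the 2-year scan, so nobody is planned to have more than one follow-up scan.

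**Sequences acquired.** Section 8.1 lists T1, T2 fast spin echo, FLAIR, gradient echo, DTI, MPRAGE and SWAN.

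**Purpose.** Section 4.1 gives the objective: "To determine the incidence of new cerebral infarct and new cerebral microbleeds using cerebral MRI in AF patients treated with Apixaban vs warfarin". Sections 1.1 and 4.1 hypothesise that fewer new infarcts and microbleeds are the route by which apixaban slows cognitive decline.

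**Analysis.** Section 9.4.1: "Cox proportional hazards model will be used to assess the secondary end points of MCI/dementia, cerebral infarction and cerebral microbleeds". The midpoint rule for dating onset in that section covers MCI/dementia only.

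**Rank.** The MRI outcome is secondary in Sections 1.1, 4.1 and 9.1 and tertiary in the Section 3 table.

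**The concern.** The objective needs a lesion marker that accumulates: whatever formed between the scans should still be identifiable at the second one. The definition names a single marker, brightness on a diffusion sequence. If that brightness is transient, the follow-up scan looks back only as far as the brightness lasts.

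The expected number of qualifying lesions per participant is then roughly the infarct rate multiplied by the duration of brightness. It does not grow with follow-up, so two years of treatment would yield about as many countable infarcts as a few months.

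What is at stake is the interpretation of the mechanism. A finding of no difference in new infarcts would be the expected result of the rule whether or not the drugs differ, yet it could be read as evidence against the proposed pathway.

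**Working it through.** **Plan's own figure.** The documents give no infarct rate, detection rate or power for the MRI endpoint, so there is nothing to reproduce. The only power statement (Section 9.2) concerns the cognitive score. It checks: 0.05 / (0.16 × √(2/140)) − 1.645 = 0.97, which is power of 83.4% one-sided, consistent with the stated figure of more than 80%. I use its 140 per arm.

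**Inputs.**
- From the documents: DTI-only definition; one follow-up scan about 730 days (104 weeks) after baseline; 140 per arm.
- Assumed: brightness lasts *w*; infarcts arise evenly over follow-up; 2-year risks of 30% v 15% or 20% v 10%; under full capture, every infarct leaves a lasting mark. None of these is in the documents.

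**Step 1. Share of infarcts still bright at the scan** = *w* / 730.5 days.

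| *w* (days) | Share counted |
|---|---|
| 7 | 1.0% |
| 14 | 1.9% |
| 28 | 3.8% |
| 60 | 8.2% |
| 90 | 12.3% |
| 180 | 24.6% |
| 365 | 50.0% |

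From 1 week to 3 months, 88% to 99% would not qualify. Brightness would have to last about a year for half to be counted. Moving the scan to 21 or 27 months changes the 14-day figure to 2.2% or 1.7%, and the 90-day figure to 14.1% or 11.0%. An exit scan at 1 year raises the share (90 / 365.25 = 24.6%), but only because fewer infarcts have had time to form; the expected number counted does not rise.

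**Step 2. Expected participants with an event** = 140 × risk × share, with share = weeks / 104. For 30% at 2 weeks: 140 × 0.30 × 0.0192 = 0.8.

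**Step 3. Power**, Fisher's exact test, two-sided 0.05, summed over the two binomial distributions. The normal approximation is not usable at these counts.

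| Capture | Events, 30% v 15% | Power | Events, 20% v 10% | Power |
|---|---|---|---|---|
| Full | 42 v 21 | 83% | 28 v 14 | 59% |
| 2 weeks | 0.8 v 0.4 | 0.01% | 0.5 v 0.3 | 0.002% |
| 4 weeks | 1.6 v 0.8 | 0.3% | 1.1 v 0.5 | 0.05% |
| 8 weeks | 3.2 v 1.6 | 2.7% | 2.2 v 1.1 | 0.8% |
| 13 weeks | 5.3 v 2.6 | 7.2% | 3.5 v 1.8 | 3.3% |

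With 140 per arm, 5 v 0 gives p = 0.060 and 6 v 0 gives p = 0.030, so significance needs a split at least as extreme as 6 v 0. At 2 weeks with 30% v 15%, the chance of no event in either arm is (1 − 0.00577)^140 × (1 − 0.00288)^140, about 30%.

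**The case against.** **The blinded radiologist will use the other sequences and compare with baseline anyway.** This has some force. Section 3 schedules scans at both times to look for new lesions, which implies a comparison, and Section 8.3.11 has the study radiologist analyse the sequences in more detail than the clinical report. Loose drafting is also plausible: the sequence numbering skips an item, and microbleeds are assigned to SWAN in Section 3 but to GRE and MPRAGE in Section 8.1. So a reader might infer that nearly all infarcts will in fact go uncounted, or that new can only mean recent at the scan. The documents do not support either as a certainty; they support only what the rule would do if applied as written. But the comparison that Section 3 implies is still of DTI lesions, and no section gives FLAIR, T2 or T1 a role in identifying infarcts. If readers use them informally, the endpoint depends on the reader, and the text still needs changing.

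**Duration of brightness is an outside input.** True, as are even onset and the risks. The power figures are illustrations. The direction is robust: the rule would capture most infarcts only if brightness lasted more than about a year.

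**The endpoint is minor and was never powered.** A reader might infer that the trial's main conclusion is at risk. It is not: the primary hypothesis and sample size (Sections 9.1 and 9.2) rest on the global cognitive score. Still, low power through sample size differs from a rule that discards most of the events, and silent infarcts appear in the trial title and the stated mechanism.

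**Conclusion.** The mismatch stands as a defect of the written definition. One DTI criterion and one follow-up scan cannot measure 2-year incidence if DTI brightness is short-lived. For assumed durations of 1 week to 3 months with even onset, about 1% to 12% of infarcts formed during follow-up would qualify. Under the illustrative risks, power drops from about 83% to 0.01–2.7% (30% v 15%), and from about 59% to below 1% (20% v 10%), for durations of 2 to 8 weeks. It is still only about 7% and 3% at 13 weeks. The full-capture figures are upper bounds, because some infarcts may leave no lasting mark.

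A null infarct result would therefore be uninformative about the hypothesis in Sections 1.1 and 4.1. The effect is confined to the MRI infarct endpoint, so this is a should-fix and not a threat to the primary analysis.

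**What to change.** 1. **Sections 8.1 and 3:** define a new infarct as a focal lesion with infarct characteristics on FLAIR/T2 and T1/MPRAGE at 2 years or exit that is absent at the same location on that participant's baseline scan. State that the blinded radiologist reads the two scans side by side. Keep DTI only to flag a lesion as recent.
2. **Section 9.4.1:** replace the ordinary Cox model for this endpoint with a binary or count analysis, or an interval-censored model that allows for exit scans at different times. Onset between two scans is unknown, and no dating rule covers it.
3. Use the same edit to give the MRI outcome one rank, secondary or tertiary, throughout.

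The cost is wording in three sections and the reading form, plus slightly more reading time per follow-up scan. No scan, sequence or reader is added. The images are already planned at both visits, so little is lost if the change is made before blinded reading starts.
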